## **Study Protocol**

### ***Study design***

This parallel-group RCT was designed to compare retention days in residential treatment among participants randomly assigned to one of two study conditions as adjuncts to their residential SUD treatment: (1) MMWR and (2) Neurobiology of Addiction (NA), with the latter serving as the psychoeducational control condition. Baseline interviews occurred prior to randomization and post-intervention interviews occurred up to 14 days after the last class session of the study intervention. All participants received SUD treatment services as normally provided by the treatment facility without affecting the level of usual care provided to patients. The study site offered no structured mindfulness-based activities or services during the study period. The University of Southern California Institutional Review Board approved this study (UP-14-00391).

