Power analysis yielded an estimated sample size of 200 to 225 needed to detect a medium-sized effect (hazard ratio = 0.52 to 0.54) for residential treatment retention using a log-rank test with a two- sided 5% significance level and 80% power, given the probability of remaining in the treatment program in the control group is 50%. We conducted standard statistical diagnosis and performed descriptive analyses of background variables, assessed variable distributional properties, plotted means of the continuous outcome variables at each time point, and assessed internal consistency and test-retest reliability of study scales. We verified the adequacy of randomization on demo- graphic and clinical covariates, and identified variables found to differ between groups at $p < .20$ (Table 1) to include them as model covariates. Based on this criteria, the covariates included in all adjusted models were number of mental health diagnoses (i.e., SUD only, 1 co- morbid mental health dx, 2 + comorbid mental health dx), adulthood trauma exposure (LSC-R), PTSD diagnosis by DSM-5, and PTSD symptom score (PSS-SR), as well as a study design feature (i.e., days in residential treatment prior to study intervention start date obtained from clinic records) to account for exposure to residential treatment prior to the start of our study intervention.

To examine the differential risk of the outcome event (i.e., patient left treatment before completion of the treatment plan and made little or no progress toward achieving treatment goals based on clinical team determination), we applied Kaplan-Meier survival analysis using an intent-to-treat (ITT) approach with time starting on the first day of the study intervention and

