ending 150 days later. Participants with the discharge status of completer, non-completer with significant progress, and in-residence were coded as 1 for “retention”. Participants with the discharge status of non-completers without significant progress were coded as 0 for “non-retention”. Our examination of the survival curves revealed that group curves crossed at 50 days from the start of the intervention, which indicated the need for a piecewise model. Thus, a multivariable, 2-piece model (i.e., Piece 1 predicting outcome events during day 0 to 50 and Piece 2 predicting outcome events for days 51 to 150) was calculated. The first piece of the model coincided with the study intervention period and the second piece to the post-intervention period. Adjusted Cox proportional hazards regression (PROC PHREG), with days as the time scale, provide estimates of hazard ratios (HR) and the 95% confidence intervals (CI) for the non-retention outcome event. HR effect size estimates are categorized as small (0.77), medium (0.53), and large (0.36) (Amaro et al., 2016). We conducted logistic regression (PROC LOGISTIC) to test for group differences in satisfactory progress among the subgroup of non-completers. We used general linear mixed models (PROC MIXED) to examine differential changes in the self-reported mechanism of action variables from pre-intervention to post-intervention by group, adjusting for covariates. We used Pearson r to test for correlation between class attendance (as a dosage variable) and change in mechanisms of action measure scores. Pearson r effect sizes are small (.10), moderate (0.30), or large (0.50). All analyses were conducted in SAS version 9.4 (SAS Institute). All models used a maximum likelihood estimated approach to account for missingness.

Substance Use and Relapse

To quantify substance use at the three assessment points (baseline, postintervention, and follow-up), our trained study staff used the TLFB measure, which is a comprehensive retrospective calendar-based validated semistructured interview measure of daily substance use (29). From TLFB data, we calculated substance use from study intervention start date

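### Mechanism outcomes are compared on pre-to-post change with no stated adjustment for each scale's own baseline score, which on the usual reading gives up precision at no gain

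*SAP*

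**What the plan says.** The SAP's first Data analysis section, which covers retention and mechanisms, gives the mechanism analysis in one sentence: PROC MIXED is used "to examine differential changes in the self-reported mechanism of action variables from pre-intervention to post-intervention by group, adjusting for covariates".

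The same section fixes the covariates: "the covariates included in all adjusted models were number of mental health diagnoses", then "adulthood trauma exposure (LSC-R), PTSD diagnosis by DSM-5, and PTSD symptom score (PSS-SR), as well as a study design feature", the design feature being days in residence before the study intervention began. Each is a baseline characteristic with one value per woman. The baseline score of the mechanism scale being analysed is not on the list. On missing data the section says: "All models used a maximum likelihood estimated approach to account for missingness".

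The Protocol (Study design) gives the timing: "Baseline interviews occurred prior to randomization and post-intervention interviews occurred up to 14 days after the last class session of the study intervention". So each mechanism scale contributes one score before and one after the intervention, and the first precedes randomization.

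Neither document gives a model equation, a covariance structure, a constraint on the baseline means or a covariate-by-time term. Neither gives an N, SD, effect size or pre-post correlation for the mechanism outcomes.

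**The concern.** A difference between arms in pre-to-post change is, in ordinary PROC MIXED usage, the group-by-time term, with each arm keeping its own baseline mean. Used this way, the baseline score enters only by subtraction. That is less efficient than using it as a covariate, or than using the fact that randomization makes the two baseline means equal in expectation.

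The covariates were chosen because the arms differed on them at p < .20, so their purpose is to deal with imbalance. As main effects in a two-time-point model they barely reach the contrast being tested. The variable whose imbalance acts on it most directly, the scale's own baseline score, is not adjusted for.

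At stake are the width of the intervals for the mechanism measures, the power to detect a mechanism effect, and how far a chance baseline difference carries into the result.

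**Working it through.** The plan states no figure for this analysis, so there is none to reproduce.

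**Inputs.** Two scores per woman and the covariate list come from the documents. The rest is assumed: 100 women per arm (the SAP gives N = 200 for the substance-use analysis only), equal SDs set to 1, and pre-post correlation r from 0.3 to 0.7, with 0.9 as a high case.

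**1. What is tested.** With complete pairs and free baseline means, the group-by-time term is (post − pre in MMWR) − (post − pre in NA), taken on arm means. A covariate main effect adds the same amount to a woman's pre and post score, so it subtracts out. A fitted example on simulated data (200 women) confirms this:

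| Model | Estimate | SE |
|---|---|---|
| Raw difference in mean change | −0.140 | – |
| Group-by-time, no covariate | −0.140 | 0.202 |
| Group-by-time, covariate as main effect | −0.140 | 0.202 |
| Group-by-time, covariate-by-time added | −0.321 | 0.196 |
| Baseline means constrained equal, no covariate | −0.102 | 0.177 |
| ANCOVA on own baseline score | −0.108 | – |

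**2. Precision.** Per woman, the variance for change is 2(1 − r) and for the baseline-adjusted score 1 − r². The ratio is 2(1 − r)/(1 − r²) = 2/(1 + r), and interval widths differ by its square root. With 100 per arm, SE = √(2/100 × variance) and the 95% half-width is 1.96 × SE.

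| r | 2(1 − r) | 1 − r² | Variance ratio | Width ratio | Half-width, change | Half-width, adjusted |
|---|---|---|---|---|---|---|
| 0.3 | 1.40 | 0.91 | 1.54 | 1.240 | 0.328 SD | 0.264 SD |
| 0.5 | 1.00 | 0.75 | 1.33 | 1.155 | 0.277 SD | 0.240 SD |
| 0.7 | 0.60 | 0.51 | 1.18 | 1.085 | 0.215 SD | 0.198 SD |
| 0.9 | 0.20 | 0.19 | 1.05 | 1.026 | 0.124 SD | 0.121 SD |

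The variance ratio is also the factor by which the sample would have to grow to recover the loss: 54%, 33% and 18% more women at r = 0.3, 0.5 and 0.7. Power for an assumed 0.4 SD effect, change against adjusted, is 67% against 84%, 81% against 90%, and 95.5% against 97.7%. Simulated SEs (4,000 trials) agree with the formulas: 0.167 against 0.133, 0.142 against 0.123, and 0.109 against 0.101.

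**3. Chance imbalance.** A baseline difference of 0.2 SD has z = 0.2/√(2/100) = 1.41, p = 0.16. It shifts the change contrast by (1 − r) × 0.2 in the opposite direction:

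- r = 0.3: 0.14 SD, or 0.14/0.167 = 0.84 SE
- r = 0.5: 0.10 SD, or 0.10/0.141 = 0.71 SE
- r = 0.7: 0.06 SD, or 0.06/0.110 = 0.55 SE

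In the simulation, the change estimate correlated −0.60, −0.50 and −0.38 with the chance baseline difference. The baseline-adjusted estimate correlated about 0.

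**4. Missing post scores.** Exact cancellation needs complete pairs. A simulation of 200 women with 20% of post scores missing at random and one prognostic main-effect covariate (300 trials at each of r = 0.3, 0.5 and 0.7) gave these results:

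- Adding the covariate moved the estimate by 0.007 to 0.018 SD on average and left its spread almost unchanged.
- The estimate still correlated −0.36 to −0.49 with the chance baseline difference.
- A constrained model with covariate-by-time terms correlated 0.0 to 0.1, with spread 0.144 against 0.178, 0.133 against 0.143, and 0.111 against 0.121.

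In a harsher single example with 69 post scores missing, the covariate moved the estimate from 0.662 to 0.625 (SE 0.155 to 0.154).

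**The case against.** The strongest reply is that the model form is inferred. One sentence names PROC MIXED and differential change; it does not say that baseline means are free or that covariates enter only as main effects. If the means were constrained equal, most of the loss would vanish (SE 0.177 against 0.202 in the example), and covariate-by-time terms would let the covariates act. This stands, and it makes the size conditional. It does not remove the point, because nothing in either document states such a constraint or such terms.

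Four stronger readings are tempting and are not supported:

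- **That the plan ignores its covariates.** It states that it adjusts for them, and they are in the model. The narrower fact is that main effects cancel from this contrast with complete pairs. The plan expects missing scores, and then they act slightly.
- **That the mechanism results are biased.** Under randomization the change contrast is unbiased on average. The loss is in precision and in sensitivity to the imbalance that happened to occur.
- **That baseline imbalance in the mechanism scales is known.** The p < .20 screen is described for demographic and clinical covariates, and by chance such a screen flags about one variable in five.
- **That the baseline score is thrown away.** It is modelled as a repeated outcome, only less efficiently than it could be.

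A further objection concerns the remedy. The substance-use Data Analysis section excludes 25 randomized women who missed the first class (25/225 = 11%). If they are also excluded here, randomization no longer guarantees equal baseline means, and the constraint becomes an assumption. This stands, and the fix allows for it.

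**Conclusion.** The point holds as a free improvement to the mechanism analysis. On the usual group-by-time reading, the tested contrast has 2/(1 + r) times the variance of a baseline-adjusted one and retains part of any chance baseline difference, and the listed covariates do little to correct either. The cost runs from substantial at r = 0.3 (67% against 84% power for a 0.4 SD effect) to negligible at r = 0.9.

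The size rests on an assumed r, an assumed 100 per arm, equal SDs and a model form that the SAP does not print. A reader might infer that the trial's main conclusions are in doubt. They are not: the retention and substance-use analyses do not use this contrast.

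**What to change.** In the SAP's first Data analysis section, define the mechanism effect as the arm difference in the post-intervention score, adjusted for that scale's own baseline score and the listed covariates. Name one of two models:

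- **ANCOVA** of the post score on group, own baseline score and covariates. It drops women without a post score, and those without a baseline score unless it is imputed.
- **Constrained PROC MIXED**: time and group-by-time with no group main effect, so that arm means are equal at baseline; unstructured covariance; and covariate-by-time terms. It keeps women with only one score.

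The two are therefore not interchangeable when scores are missing. In the constrained model, keep all randomized women with a baseline score, because only in that set does randomization guarantee equal baseline means. If the first-class no-shows are excluded, state equality as an assumption or use ANCOVA.

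The cost is a few lines of SAP text, a changed MODEL statement and a re-run; no new data are needed. Because the SAP describes the analysis in the past tense, a re-run should be reported as a re-analysis beside the change contrast.

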through the day of the last intervention session date (6 weeks later) and from intervention end date to 7 months later (8.5-month follow-up period in total). The interview window for postintervention assessment was 1 to 14 days after the intervention end, and for the follow-up assessment, the window was 7–9 months after the intervention end, and this variability was dependent on participant availability. This allowed for the quantification of daily substance use from study intervention start date to study end point. TLFB data allowed us to operationalize three substance use outcomes for any drug use and alcohol to intoxication as well as methamphetamine and cannabis/marijuana, including the following: time to first use, quantified as days until first any drug use or alcohol intoxication; days of use, quantified as the total number of days in which any drugs were used or alcohol intoxication occurred, and relapse status, quantified according to a) abstinent, did not use during the period after the study intervention; b) lapse, used after study intervention but did not revert to regular use on one-third or less of days after first use; and c) relapse, used substance after the study intervention and continued to use regularly on more than one-third of days from first use.

Alcohol and Drug Use Confirmation Tests

Breathalyzer (for alcohol) and urine (for drug) samples were collected at postintervention and follow-up. We calculated agreement rates for any and each drug (excluding alcohol) against TLFB self-report. Only two participants had a positive Breathalyzer result. For urinalysis, we compared TLFB drug use reports for 3 days before the urinalysis date against the urinalysis result.

Data Analysis

Our analytic sample size of 200 was powered to detect a medium-sized effect (Cox regression hazard ratio [HR] = 0.51) for days until first drug use with a two-sided $p < .05$ significance level,

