80% power, and a 35% probability of substance use in the control group. Our ITT analysis of $N = 200$ did not include the 25 women randomized to a study group who never showed up to the first class and were thus excluded from analysis based on receiving no dose of the intervention. Prediction models included clinical covariates identified a priori as having conceptual relevance for their impact on the effect of study intervention on recovery (i.e., number of mental health diagnoses coded as SUD only, one co-morbid mental health diagnosis, two or more comorbid mental health diagnoses, adult- hood trauma exposure [summed domain score from Life Stressor Checklist Revised], PTSD diagnosis via the Diagnostic and Statistical Manual of Mental Disorders [5th Edition], and PTSD symptom score [PTSD symptom Scale Self Report]). These models also adjust for an inherent study design variable (i.e., days in residential treatment before study intervention start date). Unadjusted models as effect size confirmation is located in the online supplement. We use the piecewise Cox regression PHREG procedure in SAS version 9.4 (SAS Institute) to model time periods during and after the study intervention (i.e., piece 1 predicting outcome events during the intervention period and piece 2 predicting outcome events after the intervention). Resulting HR effect sizes are interpreted as small (0.77), medium (0.53), and large (0.36) (35). Next, because of the zero-inflated distribution of days of substance use, we use negative binomial hurdle models to estimate any use (versus abstinence) and days of use among users simultaneously (36). Finally, we compute unadjusted and adjusted proportional estimates for group differences in relapse status (i.e., abstinent, lapse, relapse), and effect size is expressed as odds ratios (ORs).

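### Baseline substance use is measured before randomisation but is not a covariate in the substance-use models; adding it could raise power at little cost

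*SAP*

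**What the plan says.** The SAP, under Substance Use and Relapse, collects the same instrument three times: "To quantify substance use at the three assessment points (baseline, postintervention, and follow-up), our trained study staff used the TLFB measure". The Protocol, under Study design, fixes the timing of the first: "Baseline interviews occurred prior to randomization". A pre-randomisation TLFB measure is therefore planned for both arms.

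The outcomes start later: "From TLFB data, we calculated substance use from study intervention start date". They are days to first use, days of use and a three-level relapse status. Each is defined for any drug use or alcohol to intoxication, and for methamphetamine and cannabis.

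The SAP's second Data Analysis section (the one on substance use) describes the covariates: "Prediction models included clinical covariates identified a priori as having conceptual relevance for their impact on the effect of study intervention on recovery". It then lists number of mental health diagnoses, adulthood trauma exposure, PTSD diagnosis and PTSD symptom score. One more follows: "These models also adjust for an inherent study design variable (i.e., days in residential treatment before study intervention start date". The list is worded as complete. Unadjusted models go to a supplement.

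**The concern.** The models for substance use adjust for mental health, trauma and time in residence, but not for earlier substance use, although the trial measures it before allocation with the outcome instrument. The SAP's stated criterion is conceptual relevance to recovery. Prior use meets it at least as plainly as the listed variables, and no reason is given for leaving it out.

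The drug-specific outcomes are the most exposed. If the sample includes women with no history of methamphetamine or cannabis use, they are likely zeros for that drug. No listed covariate separates them from former users who stayed abstinent. The documents give no drug histories, so how many such women there are is unknown.

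At stake is power in a trial of 200 analysed women. A lesser matter is comparability: the analysed set leaves out 25 randomised women, so adjustment for a strong prognostic factor would also give some protection.

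**Working it through.** **1. Where baseline use could enter**

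| Outcome | Planned model | Baseline value of its own? |
|---|---|---|
| Time to first use | Piecewise Cox | No; the clock starts at the intervention |
| Any use, days of use | Negative binomial hurdle, two parts | Yes |
| Relapse status | Adjusted proportions, odds ratios | No; defined on use after the intervention |

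The definitions are "time to first use, quantified as days until first any drug use or alcohol intoxication" for the first row and "we use negative binomial hurdle models to estimate any use (versus abstinence) and days of use among users simultaneously" for the second. Baseline use is a true baseline value in the second row only. In the other two it is a prognostic covariate.

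**2. The plan's own figure**

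Inputs (SAP, second Data Analysis section): HR 0.51, two-sided 5%, 80% power, 35% use in control, N = 200. An equal split is assumed.

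- Events (Schoenfeld) = 4 × (1.960 + 0.842)² / (ln 0.51)² = 31.4 / 0.453 = 69.3, rounded up to 70.
- N = 70 / 0.35 = 200, power 80.4%. The figure reproduces if 35% is the overall event proportion. No covariate term is involved, so adding or omitting baseline use does not change it.
- If 35% is read literally as the control proportion, the other arm has 1 − 0.65^0.51 = 19.7%. The mean is 27.4%, giving 54.7 events in 200 women and power of 70.2%. That is a separate matter. It is noted only because the simulation below uses this reading and so starts near 68% instead of 80%.

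**3. What adjustment could gain**

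The simulated hazard is λ × exp(ln 0.51 × arm + γ × x), where x is standardised baseline use. λ is set so that 35% of controls have the event. There were 100 women per arm and 4,000 trials per setting. A Cox model was fitted with and without x. The simulation error is √(0.68 × 0.32 / 4,000), about 0.7 points.

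| HR per SD of baseline use (assumed) | Power without | Power with | Gain (points) |
|---|---|---|---|
| 1.00 | 68.2% | 68.2% | 0 |
| 1.35 | 67.0% | 68.2% | about 1 |
| 1.65 | 64.1% | 68.3% | about 4 |
| 2.23 | 61.6% | 69.9% | about 8 |

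A separate run of 800 trials per setting agrees. At a log HR of 0.7 per SD, power was about 61% without and 69% with the covariate, and the mean HR was 0.53 without and 0.50 with it. At a log HR of 0.4, power was 65% without and 67% with.

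The limits of these figures are that they use a single-piece Cox model with one covariate against none. The real comparison is six covariates against five in a two-piece model, so overlap with the listed covariates would probably shrink the gain.

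**4. Exclusions after allocation**

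25 / (200 + 25) = 11% of randomised women are left out because they never came to the first class. The documents do not give their split by arm or their prior use.

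**The case against.** The strongest reply is that the gain is unproven. No document gives the association between baseline and later use, and five covariates are already in the models. Women were already in residence at the baseline interview (Protocol, Participants and procedures), so a short look-back could show little use, and the TLFB look-back period is not stated. All of this stands, and it limits what can be claimed about size.

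Second, the SAP's first Data analysis section screens demographic and clinical variables for imbalance and adjusts for those differing at p < .20; the same covariates reappear in the substance-use models. Baseline use may have been screened and found balanced. The documents do not show this either way, so it would be wrong to say that nothing guards against chance imbalance. But a balance screen does not answer the efficiency point: a prognostic covariate helps even when it is balanced.

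Third, the SAP, dated June 2021, already reports observed results: retention curves crossing at 50 days and two positive Breathalyzer tests. A covariate added now may be post hoc. That stands and shapes the fix.

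A reader might go further and infer four things that the documents do not support:

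- *The treatment effect is biased.* The shift of an HR or OR toward 1 when a prognostic covariate is omitted reflects non-collapsibility, the difference between marginal and conditional effects. It is not bias under randomisation.
- *Power is certainly lost.* It is lost only if prior use is prognostic beyond the listed covariates.
- *Every outcome lacks adjustment for its own baseline.* Only any use and days of use have one.
- *The loss converts to an equivalent sample size through 1 − r².* That formula is for a linear outcome, and none of the planned substance-use models is linear.

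**Conclusion.** The point holds as a missed efficiency gain. A pre-randomisation measure from the outcome instrument is collected and is not among the covariates listed for the substance-use models. If it is prognostic beyond the five listed covariates, adding it would raise power and precision. In the Cox model and the any-use part, the gain appears mainly as an effect further from 1 relative to its standard error, not as a narrower interval.

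The plausible gain in Cox power is 0 to about 8 points. This rests on an assumed HR of 1.00 to 2.23 per SD, a 35% control proportion, an equal split and no other covariates. The actual figure cannot be computed from the documents. When prior use was not prognostic, adjustment cost nothing visible in the simulation.

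The stated N of 200 neither relies on this covariate nor changes with it. The 11% excluded after allocation give a modest further reason to adjust, because the analysed groups are not exactly the randomised ones. The documents do not show any resulting imbalance in prior use.

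**What to change.** Add baseline TLFB use to the piecewise Cox model, both parts of the hurdle model and the adjusted relapse-status model. Match it to the outcome: any drug use or alcohol intoxication for the overall outcomes, and methamphetamine or cannabis days for the drug-specific ones. A workable form is log(1 + days used) over the available baseline window, preferably a fixed period before residential admission if the TLFB reaches back that far. The SAP should state that window.

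If outcome results have already been seen, keep the planned model and report the adjusted one beside it as a labelled sensitivity analysis.

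The cost is a short SAP addition, one more parameter in each model part, and a stated rule for any missing baseline TLFB. No new data collection is needed to use the existing window.

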Women's Treatment and Early Recovery (MBRP-W)

NCT02977988

June 02, 2021

Statistical Analysis Plan

Measures for data capture

Discharge Status. Following routine site protocol, the SUD site treatment team (i.e., certified SUD counselor, masters-level clinician therapist, and team supervisor masters-level therapist; the latter two registered with the Board of Behavioral Sciences) decided on a case-by- case basis if a client developed the necessary skills to complete residential treatment. One of three clinical progress designations was documented in a patient's chart at discharge based on their progress. *Completer:* patient completed course of treatment, met treatment goals and were sufficiently stable (i.e., developed sufficient coping skills, attended groups, adhered to requirements on days away from the facility such as calling in, returning on time and negative drug screen) to transition to stepped-down care. *Non-completer with satisfactory progress:* patient left treatment before completion of the treatment plan and be- fore achieving all treatment goals, but deemed by the clinical team as having made important progress toward treatment goals and improved stability. *Non-completer without satisfactory progress:* patient left treatment before completion of the treatment plan and the clinical team determined that little or no progress was made toward achieving treatment goals (i.e., left early in treatment without being able to re- ceive many services, administratively discharged due to multiple oc- casions of relapse as assessed by drug screens without changes in be- havior, repeatedly violated residential treatment rules such as bringing drugs on site). *In-residence:* patient remained in treatment at the residential treatment facility at the end of the analytic period (i.e., day 150). It was not possible to blind the discharge team to group assignment; however, the study was presented to the discharge team as a test of two alternative intervention approaches in an effort to prevent any unbalanced expectation of treatment benefit.

Days until discharge. We used site discharge records to calculate the number of days in residential treatment beginning from the study intervention start date (day 0) and ending at day 150. We selected an analytic time period to approximate the average length of stay at the SUD treatment site (5.5 months).

Data analysis

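### Missing TLFB interviews are treated as ignorable given baseline data alone, although site records of discharge status and date to day 150 could inform the substance-use analyses

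*SAP*

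**What the plan says.** **Source of the use data.** Under Substance Use and Relapse, the SAP derives time to first use, days of use and relapse status from TLFB interviews. The last interview falls 7–9 months after the intervention ends, and "this variability was dependent on participant availability". Breath and urine samples are taken at the same assessments and serve only as an agreement check (Alcohol and Drug Use Confirmation Tests).

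**Missing data.** The only statement is the last sentence of the retention analysis (SAP, first Data analysis section), which says that all models relied on maximum likelihood. The substance-use sections give no censoring date, no coding rule for a woman without a follow-up interview, and no sensitivity analysis for missing interviews.

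**Conditioning variables.** The use models contain comorbid diagnoses, adult trauma exposure, PTSD diagnosis and PTSD symptoms. "These models also adjust for an inherent study design variable (i.e., days in residential treatment before study intervention start date"). Nothing recorded after the start of the intervention is included.

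**What is known without an interview.** Under Days until discharge: "We used site discharge records to calculate the number of days in residential treatment", counted to day 150. Under Discharge Status, each woman is classed as completer, non-completer with or without satisfactory progress, or still in residence at day 150. One example given for the worst class is repeated "relapse as assessed by drug screens".

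**The concern.** By the follow-up interview, at least about 8.5 months after the intervention starts, many women will have left: the protocol gives an average stay of 5.5 months (Study site standard care). For a woman who has left and is not interviewed, no planned source covers her later use.

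The analysis is unbiased only if missing an interview is unrelated to use, given the variables in the model. This holds on either reading of the SAP. Maximum likelihood assumes data missing at random given the modelled variables. If that sentence does not reach the use models, the usual defaults are non-informative censoring or complete cases. Both leave out how and when a woman left, which the SAP itself links to relapse and which plausibly affects whether she can be found.

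Two quantities are at stake: the absolute level of use, and the contrast between arms. They behave differently, as the check shows.

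**Working it through.** **The plan's own figure.** The use analysis is planned on 200 women, HR 0.51, a two-sided 5% test, and "80% power, and a 35% probability of substance use in the control group". By Schoenfeld's formula with 1:1 allocation (assumed; the ratio is not stated), events = 4 × (1.960 + 0.842)² / (ln 0.51)² = 31.4 / 0.4534 = 69.2, so 70, and 70 / 0.35 = 200. The figure reproduces if 35% is the event probability over both arms. It contains no allowance for missing interviews. (If 35% applies to the control arm only, as worded, power at 200 is about 70%; that is a separate matter.) The documents give no missing-interview rate, so everything below is illustration.

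**Illustration 1: interview depends on discharge status.**

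Inputs from the SAP:
- 50% of controls remain in treatment (retention power statement), read here as L = 0.50 leaving without progress.
- The SAP's medium HR of 0.53 gives MMWR L = 1 - 0.5^0.53 = 0.307.
- Control use is 35%.

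Assumed:
- Use is 55% in leavers and 15% in others, chosen so that 0.5 × 0.55 + 0.5 × 0.15 = 0.35.
- 90% of non-leavers are interviewed, and a fraction f of leavers.

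True MMWR use = 0.307 × 0.55 + 0.693 × 0.15 = 27.3%, so the true difference is -7.7 points. The approximate HR is ln(1 - 0.273) / ln(1 - 0.35) = 0.74.

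Observed use = [L·f·0.55 + (1 - L)·0.9·0.15] / [L·f + (1 - L)·0.9].

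| Leavers interviewed, control / MMWR | Observed use, control / MMWR | Difference (points) | Approx. HR |
|---|---|---|---|
| All women interviewed (truth) | 35.0% / 27.3% | -7.7 | 0.74 |
| 60% / 60% | 31.0% / 24.1% | -6.9 | 0.74 |
| 70% / 40% | 32.5% / 21.6% | -10.9 | 0.62 |
| 40% / 70% | 27.3% / 25.3% | -2.0 | 0.91 |

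Worked control value, second row: (0.5 × 0.6 × 0.55 + 0.5 × 0.9 × 0.15) / (0.30 + 0.45) = 0.2325 / 0.75 = 31.0%.

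Weighting by discharge status within arm returns -7.7 in every row. That is built in, because the example lets interview depend only on arm and status. It is not evidence that weighting would be enough in the trial.

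**Illustration 2: a different model, at the use section's own HR.** True use is 35% in control and 1 - 0.65^0.51 = 19.7% in MMWR (HR 0.51). A fraction m has no interview, and those women have k times the use risk of women interviewed (k = 1.5 to 2.0, assumed). Observed use = p / (1 - m + m·k); for control with m = 0.2 and k = 1.5 this is 0.35 / 1.1 = 31.8%.

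- 20% missing in both arms: control use 31.8% to 29.2%, HR 0.516 to 0.521.
- Control 20%, MMWR 30% missing: HR 0.491 to 0.477 (effect overstated).
- Control 30%, MMWR 20% missing: HR 0.545 to 0.572 (effect understated).
- Extreme bounds, taking 35% and 19.7% as the observed rates and giving all missing women in one arm use and none in the other: HR 0.37–0.86 at 10% missing per arm, 0.26–1.35 at 20%, 0.19–2.05 at 30%.

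At k = 1 there is no bias; at k below 1, use would be overstated.

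**The case against.** **No non-response is documented.** The availability remark explains when the follow-up interview took place, not whether it did. The SAP adds that the design allowed daily use to be quantified through to the end point, and TLFB is retrospective, so a late interview can recover earlier days. This stands: the remark cannot be read as an admission of missing interviews. It does not help a woman who has no follow-up interview at all.

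**A reader might infer that use is understated as a fact.** That requires women not interviewed to use more. The link between discharge without progress and relapse makes this plausible, but no passage shows it or says that leavers were interviewed less often.

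**A reader might also infer that the bias must differ by arm because MMWR is meant to change retention.** The arithmetic does not bear this out. With equal tracing, where only retention differs, the contrast moves by 0.8 points and the HR stays at about 0.74. The larger shifts need a tracing gap between arms, and the 30 points used here are an assumption with no support in the documents.

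**Discharge data are incomplete for this purpose.** Status is classified only to day 150, when some women are still in residence, while use is followed for about 8.5 months. The data can inform the missing outcomes but cannot replace them.

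**A reader might infer that relapse discharges can simply be counted as use events.** The SAP describes a progress class and a date, but no discharge-reason variable or dated drug screens; relapse is one example among several. The discharge team was also not blinded to arm. Nor does the SAP say that a relapse-discharged woman who is not reached is censored as a non-user, since no censoring rule is given.

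What remains is that a recorded, plausibly predictive variable is left out of the only stated approach to missing data, and no analysis tests that approach.

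**Conclusion.** The concern holds in a limited form. The use analyses rest on missing interviews being ignorable given baseline covariates and pre-study residential days, although discharge status and date to day 150 are available without an interview.

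Absolute use is probably understated, on the assumption that women who left without progress are interviewed less often and use more. In the equal-tracing case of the first illustration, the control rate falls from 35.0% to 31.0%.

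The arm contrast is robust to loss that is equal across arms (-6.9 against -7.7 points) and sensitive to loss that is not (-10.9 or -2.0 points; in the second illustration a true HR of 0.51 becomes 0.477 to 0.572). The documents give no interview rates, so they do not show that any such bias occurred or in which direction. Interview completion by arm is the deciding fact, and the SAP does not plan to report it.

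**What to change.** 1. **Use the discharge data.** For time to first use, the hurdle models and relapse status, add an analysis that either multiply imputes missing use or weights by the inverse probability of having TLFB data. The imputation or weighting model should contain arm, discharge status and date (to day 150), any postintervention TLFB data and the baseline covariates. Discharge status belongs there and not as a covariate in the outcome model, because it arises after randomization and may be affected by arm.
2. **Go beyond missing at random.** Step 1 still assumes that reached and unreached women with the same record use alike. Add a delta-adjusted or tipping-point analysis with the shift varied separately by arm.
3. **Report completion.** Tabulate postintervention and follow-up interviews by arm and discharge status, state how a woman without a follow-up interview enters each model, and limit the conclusion if the arms differ.
4. **Optional.** Count a chart-recorded relapse discharge as a use event in a sensitivity analysis only, if its reason and date are held, and note that the discharge team was unblinded.

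Cost: SAP wording and modest programming, since discharge status and date are already used for retention, and somewhat wider intervals. Step 4 may need further data extraction.
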